# **19 PUBLICATION POLICY**

This clinical investigation will be prospectively registered at a public clinical trial registry, ClinicalTrials.gov.

A joint peer-reviewed publication authored by the clinical investigator(s) and Sponsor will be prepared. In addition, the results of the clinical investigation may also be disseminated as conference presentations (for example, abstract and poster session). Manuscript authorship and responsibilities will be discussed and agreed upon prior to investigation start and in accordance with guidelines and recommendations provided by

the International Committee of Medical Journal Editors (ICMJE) to enable communication within 12 months of the Clinical Investigation Report (CIR) approval. All contributors who do not meet the criteria for authorship will be listed in an acknowledgments section of the publication.

# **20 STATEMENTS OF COMPLIANCE**

This clinical investigation shall be conducted in accordance with ethical principles that have their origin in the Declaration of Helsinki, International Standard ISO 14155:2020 Clinical investigation of medical devices for human subjects - Good Clinical Practice, 21 CFR Parts 812, 50, 54, 56 & 11, and any other regional or national regulations, as applicable.

# 21 QUALITY CONTROL AND ASSURANCE

In accordance with Cochlear's Quality Management System, all clinical investigations shall be conducted according to internationally recognised ethical principles for the purposes of obtaining clinical safety and performance data about medical devices.

The Sponsor employees (or designee) shall use standard operating procedures (SOPs) to ensure that clinical study procedures and documentation are consistently conducted and compliant with the ISO 14155 Standard, Good Clinical Practice (GCP), and applicable local regulations as noted in section 20 above.

# 21.1 Monitoring

The Sponsor will perform on-site and remote monitoring visits as frequently as necessary to oversee conduct, data collection and record keeping by sites. The clinical investigation monitoring plan is a separate document for the sponsor to follow, describing all the activities performed during site qualification, initiation, monitoring, and close out.

In accordance with applicable regulations, GCP, and sponsor's/CRO's procedures, monitors will contact the site prior to the start of the study to review with the site staff the CIP, study requirements, and their responsibilities to satisfy regulatory, ethical, and sponsor's requirements. When reviewing data collection procedures, the discussion will also include identification and documentation of source data items.

The sponsor/designee will monitor the site activity to verify that the:

- Data are authentic, accurate and complete
- Safety and rights of subjects are being protected
- Study is conducted in accordance with the currently approved CIP
- Any other study agreements, GCP, and all applicable regulatory requirements are met.

The investigator and the head of the medical institution (where applicable) agrees to allow the monitor direct access to all relevant documents.

# 21.2 Audits

To ensure compliance with GCP, the CIP, study procedures and applicable regulatory and EC requirements, an independent audit of the study may be conducted. The investigator/institution will be informed of the outcome for audits involving their site.

In addition, inspections by regulatory health authority representatives and EC(s) are possible. An Investigator must, in reasonable time, upon request from a relevant health authority or regulatory agency, permit access to requested records and reports, and copy and verify any records or reports made by the Investigator. Upon notification of a visit by a regulatory authority, the Investigator will contact the Sponsor immediately.

The Investigator will grant the Sponsor representatives the same access privileges offered to relevant health authority or regulatory agents, officers, and employees, for the purposes of a Sponsor audit of the site, or in preparation for an inspection.

Audits and inspections may occur at any time during or after completion of the study.

# 22 TRADEMARKS AND COPYRIGHT

ACE, Advance OffStylet, AOS, Ardium, AutoNRT, Autosensitivity, Baha, Baha SoftWear, BCDrive, Beam, Bring Back the Beat, Button, Carina, Cochlear, 科利耳, コクレア, 코클리어, Cochlear SoftWear, Contour, コントゥ ア, Contour Advance, Custom Sound, DermaLock, Freedom, Hear now. And always, Hugfit, Human Design, Hybrid, Invisible Hearing, Kanso, LowPro, MET, MP3000, myCochlear, mySmartSound, NRT, Nucleus,Osia, Outcome Focused Fitting, Off-Stylet, Piezo Power, Profile, Slimline, SmartSound, Softip, SoundArc, True Wireless, the elliptical logo, Vistafix, Whisper, WindShield and Xidium are either trademarks or registered trademarks of the Cochlear group of companies. © Cochlear 2022

# 24 CHANGE HISTORY.

Version	Change	Rationale
1	Initial Release	NA
2	Changed references of Approved Medical Device on Test (AMDT) to Investigational Medical Device (IMD)	Due to internal requirements on the classification of the devices that is being studied outside of approved indications.
3	Revised sections 9.2.2.2 and 9.3.2.2 regarding secondary endpoint PTA being collected at 4-weeks post-surgery	Error noted in the body of the document regarding the timing of this secondary endpoint; correct in the synopsis
4	Migrated to new template. Added references to relevant parts of 21 CFR for compliance. Changed Legally Authorized Representative to Legal Guardian throughout. Commercial labelling and device manufacturing information added to section 5.1. Withdrawn changed to discontinued in section 7.2.5. Screening/eligibility section added to section 7.3. Greater descriptions of screening requirements included. Description of the Device Use Questionnaire included in section 7.3.2.3. Updated detailed visit descriptions to include that the questionnaires are completed interview-style. Removed visit windows section 7.4.3. Added risks to study device use in section 8.2.3. Added risk mitigation for risks to study device use in section 8.4. Updated adverse event and device deficiency definitions. Added definition of Serious Health Threat in section 11.1.8. Added section 11.2.5 Non- Reportable Adverse Events. Section 12 updated for explant return procedures. Section 12 updated to change contact person. Section 14 updated to include database lock procedures. Section 22.1 expanded with further monitoring details. Exclusion criteria added. Risks of simultaneous procedures incorporated added in section 8.2.4.	New template released to reflect changes required from the ISO 14155:2020 update. Clarified items to reflect actual practice. Update to study personnel. FDA recommendations

Version	Change	Rationale
5	Change in study safety monitor.	Change in study personnel.
	Update to formatting for section 6 header.	Error in formatting in previous version.
	Updated applicable section references throughout the document.	Errors found in references.

# APPENDICES

# APPENDIX 1: STATEMENT/DECLARATION OF DEVICE CONFORMITY

# **Version History**

Version	Version Date	Author/Title	Summary of Key Changes
0.1	07Dec2020		Initial Release
0.2	19Jan2021		Revised due to 16Dec2020 FDA Study Design Considerations
1.0	09Aug2021		Updated version numbering to align with eTMF system. Updated time point for PTA secondary endpoint.

Statistical Analysis Plan			ge 3 of 13
Sponsor	Study		Version
Cochlear Americas	, , , , , , , , , , , , , , , , , , , ,		1.0

#### 1 Introduction

This statistical analysis plan (SAP) describes the planned statistical methods to be used during the reporting and analysis of data collected under the Clinical Investigation Protocol CAM5766, A pivotal, prospective, multi-center, open-label study evaluating the safety and effectiveness of the Osia 2 System in a pediatric population. This SAP should be read in conjunction with the study clinical investigation plan (CIP) and case report forms (CRFs). This version of the SAP has been developed with respect to the Clinical Investigation Protocol Version 3.0, 05AUG2021. Any revisions to the protocol or CRFs that impact the planned analyses may require updates to the SAP.

## 2 Study Objectives

The clinical investigation is a pivotal, prospective, multi-center, open-label clinical investigation evaluating the safety and effectiveness of the Osia 2 System in a pediatric population. The primary intent for this study is to support regulatory approval for the Osia 2 System in this population.

Specific objectives of the study are as follows:

#### **Primary**

 To demonstrate the safety of the Osia 2 System in a pediatric population aged 5 – 11 years by quantifying the type, frequency and severity of adverse events

#### Secondary

- To compare preoperative performance compared to postoperative performance in parental questionnaires using the Osia 2 System.
- To compare preoperative unaided bone conduction thresholds to postoperative unaided bone conduction thresholds.
- To compare unaided preoperative speech perception performance to aided speech perception performance postoperatively using the Osia 2 System.
- To compare unaided preoperative adaptive speech in noise performance to aided adaptive speech in noise performance using the Osia 2 System.

St	atistical Analysis Plan	Pa	ge 6 of 13
Sponsor	Study		Version
Cochlear Americas	A pivotal, prospective, multi-center, open- label study evaluating the safety and effectiveness of the Cochlear ™ Osia ® 2 System in a pediatric population		1.0

## 2.1 Study Endpoints

There is one primary and four secondary endpoints defined for this study.

## 3 Study Design

This is a prospective, multi-center, open-label clinical investigation. Expected enrollment is 12 months with an expected duration per subject of 12-18 months.

### 4 Sample Size Determination

Sample size for the study is not driven by power requirements for a formal statistical hypothesis test. The planned sample size of 50 subjects will provide data to characterize safety and effectiveness with a reasonable degree of statistical precision. Additionally, the planned sample size will allow for a high probability of observing events of interest. For example, with 50 subjects, the half-width of a two-sided 95% confidence interval for a continuous endpoint based on a t-distribution would be 0.284 units on the effect size scale. Similarly, with 50 subjects, there is a greater than 95% probability of observing one or more events that occur at a population rate of 5.9%

## 5 Statistical Analyses

#### 5.1 General Considerations

Except where otherwise specified, the following general principles apply to the planned statistical analyses. All statistical analysis will be conducted using SAS version 9.4 or later (SAS Institute Inc., Cary, NC) or other widely-accepted statistical or graphical software as required.

### 5.1.1 Descriptive Statistics

Continuous data will be summarized with mean, standard deviation, median, minimum, maximum, and number of evaluable observations. Categorical variables will be summarized with frequency counts and percentages. Confidence intervals may be presented, where appropriate, using the t-distribution for continuous data and Clopper-Pearson Exact method for categorical variables.

#### 5.1.2 Visit Windows

Unless otherwise specified, visit based assessments will be analyzed for each analysis time point according to the nominal visit entered in the Case Report Form (CRF) regardless of if it is out of window. Windows are defined in the CIP as follows: Visit 1 2 week follow up = +/- 7 days, Visit 2 Device Fitting = +/- 7 days; Visit 3 3 Months +/- 14 days, Visit 4 6 months +/- 14 days, and Visit 5 12 Months +/- 14 days.

St	atistical Analysis Plan	Pa	ge 7 of 13
Sponsor	Study		Version
Cochlear Americas	A pivotal, prospective, multi-center, open- label study evaluating the safety and effectiveness of the Cochlear ™ Osia ® 2 System in a pediatric population		1.0

#### 5.1.3 Statistical Significance

Unless otherwise specified, hypothesis testing will be performed at the two-sided 0.05 significance level. P-values will be rounded to three decimal places. If a p-value is less than 0.001 it will be reported as "<0.001". If a p-value is greater than 0.999, it will be reported as ">0.999".

## 5.2 Analysis Populations

Analysis will be based on subjects who are successfully implanted with the device.

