### 6.3.3 Safety Evaluations and Procedures

Safety data will be reviewed in accordance with the Sponsor's standard operating procedures regarding safety events. The risks and anticipated ADEs for the Osia 2 system, as identified in Sections 7.2 and 7.3 below, will be assessed in the clinical investigation via reporting of all AEs/ADEs from the time of subject implantation until subject last visit. Ongoing SAEs and SADEs will be followed for an additional 30 days, or until resolution or stabilization within the 30-day period following End of Study. Management of the SAE/SADE beyond clinical investigation completion will be absorbed into standard clinical and medical care by the participating clinical investigational site.

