### 7.2.1 Risks Associated with the Surgery

- General risks associated with surgery including pain, scarring, bleeding and infection.
- General risks associated with anesthesia during the surgery (e.g., risks for the heart, lungs, kidneys, liver, and brain) which, in rare cases, can result in death.

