### 8.2 Endpoints

### 8.2.1 Primary Endpoint

The primary endpoint is adverse events and serious adverse events Surgery through Visit 4 (6 Months). Events will be summarized by type, frequency, and severity.

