## 5.4 Subject Disposition

The number of subjects in each analysis population will be presented along with reason for any exclusions. Subject accountability will be summarized by visit. The number of subjects who are enrolled, eligible for follow-up, and number completing clinical follow-up will be summarized for each protocol-required visit. In addition, the number of subjects who complete the study or exit early will be summarized by reason.

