#### 5.6.1 Primary Endpoint

The primary endpoint is device and procedure related adverse events Surgery through Visit 4 (6 Months). Events will be summarized by type, frequency, and severity.

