## 5.7 Poolability Analyses

All investigational sites will follow the requirements of a common protocol and standardized data collection procedures and forms. The primary and secondary endpoints will be presented separately for each site using descriptive statistics. Poolability of the primary endpoints across investigational sites will be evaluated using a regression model with fixed effects for site. For the primary endpoint, analysis will be based on the proportion of subjects experiencing a procedure or device related adverse event and a logistic regression approach. For the secondary endpoint, a linear regression approach will be used. If the p-value for the site effect is 0.15, additional exploratory analyses will be performed to understand any variations in outcomes by site.

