## 5.8 Safety Analyses

Adverse events (AEs) will be tabulated with the number of events and subjects with event for each event type and overall. Rates will be reported as the number of subjects who experience at least one event during the analysis interval out of the total number of subjects with follow-up to the beginning of the analysis interval. Serious adverse events (SAEs) will also be tabulated.

All AEs and SAEs will also be summarized by relatedness as described above. Adverse events leading to death or study discontinuation will be provided in listing format.

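### The primary safety endpoint counts only successfully implanted children, so harm in an implant surgery that does not succeed is left out

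*SAP*

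**What the plan says.** SAP 5.2 is one sentence: "Analysis will be based on subjects who are successfully implanted with the device". Protocol 8.5 has the same sentence. Neither limits it to effectiveness, neither says when an implantation counts as successful, and neither defines a safety, treated or surgery-attempted population.

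The primary endpoint starts at the operation in both documents. Protocol 8.2.1: "The primary endpoint is adverse events and serious adverse events Surgery through Visit 4 (6 Months". SAP 5.6.1: "The primary endpoint is device and procedure related adverse events Surgery through Visit 4 (6 Months". The SAP models for site and subgroup effects (5.7, 5.9) use the "proportion of subjects experiencing a procedure or device related adverse event". The sections on the primary analysis (protocol 8.6.1, SAP 5.6.1.1) name no other population.

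Protocol 7.2.1 lists "General risks associated with anesthesia during the surgery" among the foreseen risks, and 7.2.2 lists failure of the implant to anchor in the bone.

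The protocol gives two starting points for adverse event recording. Section 6.3.3 calls for "reporting of all AEs/ADEs from the time of subject implantation until subject last visit", and 10.2 and 10.2.5 also start at implantation. The Schedule of Events, 6.1.1, 6.3.4.10 and 8.2.1 start at Surgery.

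**The concern.** Successful implantation is a result of the surgery. Using it to decide who is analyzed lets the outcome of the operation determine who is counted for harm caused by that operation. Procedure-related harm can occur whether or not the device ends up in place, and an operation may be abandoned because of such harm.

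The primary objective is to demonstrate safety in children aged 5 to 11 years, and the result is meant to support a wider pediatric indication. A descriptive primary endpoint consists of its numerator and denominator. Under the stated rule the rate describes successful implants, while a reader would take it to describe all children operated on. With about 50 children, a single case can decide whether a particular surgical harm appears in the primary table at all.

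**Working it through.** **1. The plan's own figures.** SAP section 4 and protocol 8.4 use n = 50.
- Probability of at least one event at a rate of 5.9%: 1 − (1 − 0.059)^50 = 0.952, which agrees with the stated figure of more than 95%.
- Half-width of the 95% CI: t(0.975; 49)/√50 = 0.284, as stated.

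Both figures reproduce. They take all 50 children as analyzed. If 50 operations are started and one child is excluded, the first becomes 1 − 0.941^49 = 0.949, just under 95%.

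**2. Does any other text bring the excluded child back?**
- SAP 5.4: "The number of subjects in each analysis population will be presented along with reason for any exclusions". This shows that a child was excluded and why. It does not put that child's events into the endpoint.
- Protocol 8.7 and SAP 5.8: the denominator for rates is the "total number of subjects with follow-up to the beginning of the analysis interval". Neither section says that this replaces the population in 5.2.
- The same two sections list events that lead to death or discontinuation. A listing is not the primary rate, and it does not cover other events.
- Protocol section 12 mentions a per-protocol group, which is undefined and is used only to remove data.
- Protocol 6.2.5 reserves the status Participated for children treated with the system.

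None of these restores the child to the primary result.

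**3. Size.** The documents give no rate of unsuccessful surgery, so all cases below are assumed. Let x of 50 implanted children have an event, and let one further child be operated on without a successful implant.
- If that child was harmed, adding the child changes the rate by (x + 1)/51 − x/50 = (50 − x)/2550.
- If that child was not harmed, the change is x/51 − x/50 = −x/2550.

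Intervals are Clopper-Pearson, the method named in SAP 5.1.1.

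| As written | Harmed child added | Change, points | Change if unharmed, points |
|---|---|---|---|
| 0/50 = 0% (0 to 7.1%) | 1/51 = 2.0% (0.05 to 10.4%) | +1.96 | 0 |
| 3/50 = 6.0% (1.3 to 16.5%) | 4/51 = 7.8% (2.2 to 18.9%) | +1.84 | −0.12 |
| 10/50 = 20.0% (10.0 to 33.7%) | 11/51 = 21.6% (11.3 to 35.3%) | +1.57 | −0.39 |
| 25/50 = 50.0% | 26/51 = 51.0% | +0.98 | −0.98 |
| 40/50 = 80.0% | 41/51 = 80.4% | +0.39 | −1.57 |

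If 50 operations are started and one fails with an event, the change is (x + 1)/50 − x/49:
- 0/49 against 1/50: +2.00 points
- 3/49 (6.1%) against 4/50 (8.0%): +1.88 points
- 10/49 (20.4%) against 11/50 (22.0%): +1.59 points

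**4. How likely is at least one such surgery?** With an assumed probability q per operation, 1 − (1 − q)^50 gives 39.5% at q = 1%, 63.6% at 2% and 92.3% at 5%.

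**The case against.** The strongest reply is that the practical loss is small and partly covered elsewhere.

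- **Other reporting.** A child whose operation ended in a serious event and exit from the study might appear in the listing of events leading to death or discontinuation. The exclusion would show in the disposition table. Reported events also reach the sponsor's review board and the independent monitoring committee (protocol 7.4, 10.5). This is fair and narrows the loss, but none of it enters the primary rate, and the plan does not say whether the 5.2 restriction also limits the listing.
- **Meaning of success.** Because the term is undefined, later failures such as extrusion or revision may well stay in, since the child was implanted first. The clear gap is an operation that ends with no device in place. The documents report no such case, though the study summaries in protocol 3.2.2 describe implanted subjects and so could hardly show one.
- **Event rates.** For the protocol's endpoint of all adverse events, a proportion well above 20% is plausible. The sponsor's other pediatric study recorded 15 events in 14 subjects (protocol 3.2.2.2), although the number of children affected is not given. The shift then falls below 1 point, as the last two rows of the table show. The range of 1.6 to 2.0 points suits the SAP's narrower related-event endpoint better. Every shift is small beside its confidence interval.
- **Start of recording.** Implantation can be read as meaning the surgery, and collection at Surgery is scheduled. The differing wording does not show that events on the day of surgery will be lost. It needs harmonizing but is not the core of this point.

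These replies limit the size. They do not change what the rule does when such a case occurs.

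**Conclusion.** The concern holds. Followed as written, SAP 5.2 and protocol 8.5 remove from the primary safety result any child harmed in an operation that did not end in a successful implant, although the endpoint starts at Surgery and in the SAP covers procedure-related events.

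The effect depends on two numbers that the documents do not give: how many operations are unsuccessful, and how often those children have an event. With no such operation, nothing changes. The net bias is downward only if unsuccessful operations carry a higher event proportion than successful ones, which is plausible but not shown. No hypothesis test is affected. It should be corrected because the omitted events would be surgical harm, which this endpoint is meant to capture.

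**What to change.** - **Population.** In protocol 8.5 and SAP 5.2, define a safety population of all subjects in whom Osia 2 implant surgery is started, whether or not the device is placed. State the start point. Induction of anesthesia would capture the anesthesia risks in protocol 7.2.1, whereas first incision would miss events before it.
- **Use.** Apply it to the primary endpoint (protocol 8.6.1, SAP 5.6.1), to its poolability and subgroup analyses (SAP 5.7, 5.9) and to the safety tables (protocol 8.7, SAP 5.8).
- **Secondary endpoints.** Keep the successfully implanted population for all four, and define the term.
- **Reporting.** Give the number of operations started without a successful implant.
- **Start of recording.** Bring protocol 6.3.3, 10.2 and 10.2.5 into line with the Schedule of Events, 6.1.1, 6.3.4.10 and 8.2.1.

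The cost is mainly amended wording. Event collection at Surgery is already scheduled, and SAP 5.6.1.1 works from events as observed, so such a child can be counted with the data available. One addition is needed: the plan should say how far safety data are collected for a child without a device, since protocol 6.2.6 makes safety follow-up after withdrawal a matter of permission. The reported rate may be slightly less favorable.
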